10.6.1.2 Progression-free Survival

The non-parametric Kaplan-Meier method will be used to estimate the PFS curve in each treatment group. The treatment difference in PFS will be assessed by the stratified log-rank test (based on the stratification factors defined in Section 7.3.1). A stratified Cox proportional hazard model with Efron's method of tie handling will be used to assess the magnitude of the treatment difference (ie, the HR) between the treatment arms. The HR and its 95% CI from the stratified Cox model with Efron's method of tie handling and with a single treatment covariate will be reported. The stratification factor (Section 7.3.1) based on tumor histology will be applied to both the stratified log-rank test and the stratified Cox model.

Since disease progression is assessed periodically, PD can occur any time in the time interval between the last assessment where PD was not documented and the assessment when PD is documented. For the primary analysis, for participants who have PD, the true date of disease progression will be approximated by the date of the first assessment at which PD is objectively documented per RECIST 1.1 (based on BICR), regardless of discontinuation of study drug. Death is always considered as a confirmed PD event.

In order to evaluate the robustness of the PFS endpoint per RECIST 1.1 based on BICR, two sensitivity analyses with a different set of censoring rules will be performed. For the first sensitivity analysis, participants who miss more than one disease assessment (with or without a subsequent death or progression) are censored at the last disease assessment prior to missing visits. The second sensitivity analysis handles participants who discontinue treatment or initiate an anticancer treatment subsequent to discontinuation of study-specified treatments differently from the primary analysis. The censoring rules for primary and sensitivity analyses are summarized in [Table 10](#). If a participant meets multiple criteria for censoring, the censoring criterion that occurs earliest will be applied.

Table 10 Censoring Rules for Primary and Sensitivity Analyses of Progression-free Survival

Situation	Primary Analysis	Sensitivity Analysis 1	Sensitivity Analysis 2
No PD and no death; new anticancer treatment is not initiated	Censored at last disease assessment	Censored at last disease assessment	Censored at last disease assessment if still on study therapy; progressed at treatment discontinuation otherwise

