No PD and no death; new anticancer treatment is initiated	Censored at last disease assessment before new anticancer treatment	Censored at last disease assessment before new anticancer treatment	Progressed at date of new anticancer treatment
No PD and no death; ≥ 2 consecutive missed disease assessments	Censored at last disease assessment	Censored at last disease assessment prior to ≥ 2 consecutive missed visits	Censored at last disease assessment
PD or death documented after ≤ 1 missed disease assessment	Progressed at date of documented PD or death	Progressed at date of documented PD or death	Progressed at date of documented PD or death

Situation	Primary Analysis	Sensitivity Analysis 1	Sensitivity Analysis 2
PD or death documented at any time after ≥ 2 missed disease assessments	Progressed at date of documented PD or death	Censored at last disease assessment prior to the ≥ 2 missed disease assessment	Progressed at date of documented PD or death
PD=progressive disease			

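### PFS Sensitivity Analysis 1 has conflicting missed-scan triggers: two consecutive misses without an event, any two misses before PD or death, and a narrative that fits neither row

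*Protocol*

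**What the plan says.** Protocol Section 10.6.1.2 plans two sensitivity analyses of PFS by central review. The first concerns missed scans, and its trigger is worded differently in three places.

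- **Narrative:** "participants who miss more than one disease assessment (with or without a subsequent death or progression) are censored at the last disease assessment" before the missed visits. The trigger is more than one miss, the outcome is irrelevant, and nothing says the misses must be consecutive.
- **Table 10, event-free row:** the situation is "No PD and no death; ≥ 2 consecutive missed disease assessments" and the action is "Censored at last disease assessment prior to ≥ 2 consecutive missed visits".
- **Table 10, event row:** the situation is "PD or death documented at any time after" two or more missed assessments and the action is "Censored at last disease assessment prior to the ≥ 2 missed disease assessment". The companion row counts PD or death as an event only if at most one assessment was missed.

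sSAP Section 3.6.1.2 and its Table 2 repeat all of this. The corresponding row for duration of response (Protocol Table 11, sSAP Table 3) does require the misses to be consecutive before PD or death is censored. The primary PFS analysis does not discard events because of missed scans.

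**The concern.** A participant with two isolated misses who has since returned to regular scanning meets different rows depending on what happens later. If PD is documented, the companion row is closed, because more than one scan was missed, and the event row applies: the PD is removed and follow-up is cut back. If there is no PD, the consecutive-miss row does not apply, so the default event-free row keeps follow-up to the last scan. Equal attendance is then handled differently because of the outcome, which is informative censoring.

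This analysis exists to show whether PFS is robust to missed scans, so a censoring rule tied to the outcome undermines its purpose. It also cannot be reproduced from the documents: two programmers following the table and the narrative would produce different datasets, and no order of precedence is given.

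**Working it through.** **1. The plan's only PFS design figure.** With 95 events, HR 0.6 and one-sided alpha 5% (Protocol Section 10.9.1), Schoenfeld's formula gives power = Φ(√95/2 × |ln 0.6| − 1.645) = Φ(4.873 × 0.5108 − 1.645) = Φ(0.845) = 80.1%. The stated 80% reproduces. It does not depend on the missed-scan rule.

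**2. One attendance pattern under each rule.** Assume scans every 9 weeks, done at weeks 9, 27, 45 and 54, and missed at weeks 18 and 36. (The current documents give no on-study scan schedule.)

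| Rule | PD first seen at week 54 | No PD, last scan week 54 |
|---|---|---|
| Table rows, read literally | Censored at week 9 or 27 | Censored at week 54 |
| Narrative | Censored before the misses | Censored before the misses |
| Consecutive misses required in both rows | Event at week 54 | Censored at week 54 |

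Only the literal table separates the two participants by outcome. It also leaves open which miss sets the censoring date. The rule that the earliest of several censoring criteria applies does not help, because the event-free participant meets no early-censoring row. When the two misses are consecutive, both table rows censor and there is no asymmetry.

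**3. A ceiling on the size.** Take six scheduled scans, each missed independently with probability q (assumed 5% or 10%).

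- Any two or more misses: 1 − (1−q)^6 − 6q(1−q)^5. For q = 0.05: 1 − 0.7351 − 0.2321 = 3.28%. For q = 0.10: 1 − 0.5314 − 0.3543 = 11.43%.
- At least two in a row: 1 − Σ C(7−j, j) q^j (1−q)^(6−j), j = 0 to 3. This gives 1.20% and 4.57%.
- Differences: 2.08% and 6.86%. Times 95 events: 2.0 and 6.5.

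This is too high for the trial. It treats every progressor as having had six scheduled scans before PD, and it assumes that all 95 events occur.

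**4. What the dates allow.**

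- Initial protocol 06-JUN-2017 to cutoff 10-JAN-2019: 583 days, 83.3 weeks, about 19 months at most.
- Enrollment completed 05-SEP-2018: 127 days, about 18 weeks, before cutoff.
- About 90 of the 148 were still to be randomized when Amendment 04 was being released (Protocol Section 5.2). Taking Amendment 04 to be later than Amendment 03 (05-APR-2018), those participants had at most 280 days, or 40 weeks. That allows 4 scans at a 9-week interval or 6 at a 6-week interval.

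**5. Simulation within those limits.** Assumptions: 6- or 9-week scans, 5-10% missed, control median PFS 10.3 months (the earlier Phase 3 result in Protocol Section 3.1), HR 1 or 0.6. There were about 50-64 PD events. The literal table censored about 0.4-3.9 of them and a consecutive-miss rule about 0.3-1.9, an excess of about 0.2-2 events.

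**6. Sensitivity to follow-up and miss rate.** With 3-15% of scans missed and HR 0.6:

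| Maximum follow-up | Events | Additional events censored by literal table | Largest change in mean HR against consecutive rule |
|---|---|---|---|
| 14 months | about 50 | 0.1-2.2 | 0.613 to 0.610 |
| 30 months | about 79 | 0.5-10 | 0.605 to 0.584 |

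The 30-month row lies beyond what the trial's dates permit. It shows that the effect grows with long follow-up and frequent misses.

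**The case against.** The best defence is that the table uses shorthand for a single gap. The event-row action refers to the missed assessments with a definite article, as if to one block. Table 11 requires consecutive misses in its trigger cell and then drops the word in its own action cell. The narrative, which sits directly above Table 10, is expressly indifferent to outcome. On this view the missing word is a drafting slip and no outcome-dependent rule was intended.

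Much of this stands. A reader might infer from the table alone that outcome-dependent censoring is the plan's rule. The documents do not support that, because the narrative contradicts it. But the narrative does not rescue the table: it does not require consecutive misses either, so it conflicts with the event-free row. The shorthand reading is plausible and is not stated anywhere.

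A reader might also infer that the rule favours the arm with more missed scans, or that a sizeable share of the 95 events would be lost. The documents give no miss rates by arm, and the follow-up dates rule out the larger counts at ordinary miss rates.

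Finally, this is one of two sensitivity analyses of a secondary endpoint that is tested formally only if ORR succeeds. Section 10 of the protocol records that ORR did not. That limits the consequence but leaves the specification ambiguous.

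**Conclusion.** The finding is a conflict within Table 10 and sSAP Table 2, and between both tables and the narrative. If the tables were programmed as written, Sensitivity Analysis 1 contains outcome-dependent censoring. If the narrative was programmed, it does not select by outcome but departs from the event-free row. The documents do not show which was done.

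The difference between the literal table and a consecutive-miss rule is about 0 to 2 events, with almost no change in the hazard ratio. That size rests on assumed 6- or 9-week scans, 5-10% independent misses and follow-up capped at about 19 months; more frequent misses would raise it. Nothing here suggests a changed conclusion for the trial. The ORR test, the primary PFS analysis, the alpha and the 95-event calculation are untouched. This is a minor point, worth correcting because the correction is cheap.

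**What to change.** Use one trigger in the narrative, in every relevant Table 10 row (including the row for at most one missed assessment) and in sSAP Section 3.6.1.2 and Table 2. Any participant with two or more consecutive missed assessments is censored at the last adequate assessment before the first such gap, whether or not PD or death follows. Isolated misses do not trigger censoring, so the companion row should count PD or death as an event whenever no such gap came before it.

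Do not limit event censoring to PD or death that comes immediately after a gap while leaving the event-free row as it is. A participant who misses two scans in a row, resumes and later progresses would then count as an event, while the same participant without PD would be censored back at the gap. That is the same fault in the opposite direction.

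Because the final analysis has been run, state in the sSAP or CSR which rule was programmed and which miss set the censoring date. If it was the literal table, rerun Sensitivity Analysis 1 under the single rule and report both results. The cost is a few table cells, one sentence in each document and at most one rerun. No new data are needed.

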10.6.1.3 Overall Survival

The non-parametric Kaplan-Meier method will be used to estimate the survival curves. The treatment difference in survival will be assessed by the stratified log-rank test (based on the stratification factor defined in Section 7.3.1). A stratified Cox proportional hazard model with Efron's method of tie handling will be used to assess the magnitude of the treatment difference (ie, the HR). The HR and its 95% CI from the stratified Cox model with a single treatment covariate will be reported. The stratification factor (Section 7.3.1) based on tumor histology will be applied to both the stratified log-rank test and the stratified Cox model. Participants without documented death at the time of analysis will be censored at the date of last known contact. Analysis using the Restricted Mean Survival Time method may be conducted for OS to account for the possible non-proportional hazards effect.

10.6.1.4 Duration of Response

For participants who demonstrate CR or PR, DOR is defined as the time from first documented evidence of CR or PR until disease progression or death due to any cause, whichever occurs first. Censoring rules for DOR are summarized in [Table 11](#). DOR will be assessed using RECIST 1.1 by BICR.

For each DOR analysis, a corresponding summary of the reasons responding participants are censored will also be provided. Responses in participants who are alive, have not progressed, have not initiated new anti-cancer treatment, and have not been determined to be lost to follow-up are considered ongoing at the time of analysis. If a participant meets multiple criteria for censoring, the censoring criterion that occurs earliest will be applied.

Table 11 Censoring Rules for Duration of Response

Situation	Date of Progression or Censoring	Outcome
No progression or death, new anti-cancer treatment not initiated	Last adequate disease assessment	Censor (non-event)
No progression or death, new anti-cancer treatment initiated	Last adequate disease assessment before new anti-cancer therapy initiated	Censor (non-event)
Death or progression after ≥ 2 consecutive missed disease assessments	Last adequate disease assessment prior to the after ≥ 2 missed adequate disease assessments	Censor (non-event)
Death or progression after ≤ 1 missed adequate disease assessments	Progressive disease or death	End of response (Event)
Note: A missed disease assessment includes any assessment that is not obtained or is considered inadequate for evaluation of response.		

10.6.1.5 Statistical Methods for Key Efficacy Endpoints

A summary of the primary analysis strategy for the key efficacy endpoints is provided in [Table 12](#).

Table 12 Analysis Methods for Key Efficacy Endpoints

Endpoint/Variable	Statistical Method	Analysis Population	Missing Data Approach
Primary Analyses:			
ORR (RECIST 1.1) by BICR	Testing and Estimation: Stratified Miettinen and Nurminen method	ITT	Participants with missing data are considered non-responders
Secondary Analyses:			
PFS (RECIST 1.1) by BICR	Estimation: Stratified Cox model with Efron's tie handling method Stratified Log-rank test	ITT	Censored according to rules in Table 10
OS	Estimation: Stratified Cox model with Efron's tie handling method Stratified Log-rank test	ITT	Censored at last known alive date
DOR (RECIST 1.1) by BICR	Summary statistics using Kaplan-Meier method	All responders in ITT	Non-responders are excluded in analysis
Sensitivity analyses will be performed for PFS, ORR, and DOR based on investigator's assessment. BICR=blinded independent central review; DOR=duration of response; ITT=intent-to-treat; ORR=objective response rate; OS=overall survival; PFS=progression-free survival; RECIST 1.1=Response Evaluation Criteria in Solid Tumors.			

10.6.2 Statistical Methods for Safety Analyses

As of Amendment 05, safety and tolerability will be assessed by clinical review of all relevant parameters including adverse experiences (AEs), laboratory tests, and vital signs.

Individual events and the broad AE categories consisting of the proportion of participants with any AE, a drug-related AE, a serious AE, an AE which is both drug-related and serious, a Grade 3-5 AE, a drug related Grade 3-5 AE, a fatal AE, dose interruption due to an AE and discontinuation due to an AE, will be summarized by counts and percentages by treatment group (Table 13).

Table 13 Analysis Strategy for Safety Endpoints

Safety Endpoint	Descriptive Statistics
Any AE	X
Any Serious AE	X
Any Grade 3-5 AE	X
Any Drug-Related AE	X
Any Serious and Drug-Related AE	X
Any Grade 3-5 and Drug-Related AE	X
Dose Interruption due to AE	X
Discontinuation due to AE	X
Death	X
Specific AEs, SOCs	X
Change from Baseline Results (Laboratory toxicity grade)	X

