12-Lead ECG with QTc Measurement	X	X	X					*		At screening for all participants. At select centers, also perform on C1D1 and C2D1 at predose and 120 min (±15 min) after morning dose of epacadostat/placebo. * At EOT, perform ECG per SOC or as clinically indicated.
ECOG Performance Status	X	X	X	X	X	X	X	X	X	At screening, perform within 7 days prior to Cycle 1 but before randomization.
Laboratory Procedures / Assessments: Analysis Performed by Local Laboratory										
Pregnancy Test - Urine or Serum β-HCG	X									WOCBP require negative test within 72 hours prior to Cycle 1. Test monthly if required by local regulations.
Hepatitis B & C Serology	X									Hepatitis B surface antigen, HBV-DNA, HCV-RNA (or HCV antibody if HCV-RNA is not the local SOC). May use central lab only if local lab is not capable. If this testing was conducted per SOC within 42 days prior to randomization, testing does not need to be repeated.
HIV Testing	X									Not required unless mandated by local health authority.
PT/INR and aPTT/PTT	X									Perform eligibility labs within 10 days prior to Cycle 1. Participants receiving coumarin-based anticoagulants should have more frequent INR monitoring (weekly for first 4 weeks after initiation of therapy and upon DC of epacadostat/placebo). As of Amendment 05, testing after DC of epacadostat/placebo is no longer required.
CBC with Differential	X		X	X	X	X	X	X	X	Perform eligibility labs within 10 days prior to Cycle 1. After Cycle 1, may collect up to 3 days prior to dosing.
Chemistry Panel	X		X	X	X	X	X	X	X	
Urinalysis	X		X		X		X	X	X	Perform within 10 days prior to Cycle 1, then every 2 nd cycle through Cycle 6, then every 6 th cycle thereafter (Cycles 2, 4, 6, 12, 18, etc.).

Study Period	Screen. Phase	Treatment Cycles (3-Week Cycles)						EOT	Post Treatment	Notes Participants who discontinue study treatment for whatever reason will proceed directly to EOT and Safety Follow-up.	
Treatment Cycle	Screen. (V 1)	1	2	3	4	5	6 to 35	DC	Safety Follow-up ¹		
Scheduling Window (Days):	-30 to -1	+3	±3	±3	±3	±3	±3	At DC (+3)	30 Days Post-DC (+14)		
T3/FT3, FT4, and TSH	X		X		X		X	X	X	Perform within 10 days prior to Cycle 1, then every 2 nd cycle (Cycles 2, 4, 6, 8, etc.). May use central lab only if local lab is not capable.	
Efficacy Measurements											
Tumor Imaging	X	X									The timing of imaging during the treatment phase is according to the site's SOC for tumor assessment until PD or initiation of a new anticancer regimen.

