
 • To compare PFS of the combination of pembrolizumab plus epacadostat versus pembrolizumab plus placebo. • Hypothesis (H1): The combination of pembrolizumab plus epacadostat has superior PFS compared to pembrolizumab plus placebo. • To compare OS of the combination of pembrolizumab plus epacadostat versus pembrolizumab plus placebo. • To evaluate DOR of the combinations of pembrolizumab plus epacadostat and pembrolizumab plus placebo. 	
 • PFS is defined as the time from randomization to the first documented progressive disease (PD) per RECIST 1.1 based on blinded independent central review (BICR) or death due to any cause, whichever occurs first. • OS is defined as the time from randomization to death due to any cause. • DOR defined as the time from the earliest date of qualifying response until earliest date of disease progression or death from any cause, whichever comes first, per RECIST 1.1 based on BICR.

Objective/Hypothesis	Endpoint

To evaluate the safety and tolerability of the combinations of pembrolizumab plus epacadostat and pembrolizumab plus placebo.	
Number of participants experiencing AEs and number of participants discontinuing study drug due to AEs.
	

5. Study Design

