5.5.2 Rationale for Dose and Regimen of Epacadostat in Combination with Pembrolizumab

NOTE: As of Amendment 05, this section is no longer applicable.

The dose selected for epacadostat for the current study was formed on the basis of a well-tolerated safety profile as monotherapy and in combination with pembrolizumab, efficacy evidenced by robust, durable responses, and optimal target inhibition of IDO1 based on nonclinical models.

The first-in-human study INCB 24360-101 evaluated the pharmacodynamic effects of epacadostat dose/exposure on the tryptophan pathway using an ex vivo assay optimized for determining the inhibition of the metabolism of tryptophan to kynurenine by IDO1. Epacadostat treatment produced significant dose-dependent reductions in plasma kynurenine levels and plasma kynurenine/tryptophan ratios at all doses and in all participants. Near-

maximal changes were observed at doses of epacadostat ≥ 100 mg PO BID with $>80\%$ to 90% inhibition of IDO1 achieved throughout the dosing period [Beatty, G. L., et al 2017].

In the Phase 1 portion of ECHO-202/KEYNOTE-37, epacadostat doses of 25 mg, 50 mg, and 100 mg PO twice daily (BID) in combination with pembrolizumab 2 mg/kg IV every 3 weeks (Q3W) and epacadostat 300 mg BID in combination with the fixed dose of pembrolizumab 200 mg IV Q3W were evaluated. Safety expansion cohorts also evaluated epacadostat doses of 50 mg, 100 mg, and 300 mg with the fixed dose of pembrolizumab 200 mg IV Q3W. Reductions in tumor burden were seen in 14 of 19 evaluable melanoma participants across doses of epacadostat 25 mg BID to 100 mg BID in combination with pembrolizumab 2 mg/kg and 200 mg fixed dose [Gangadhar, T. C., et al 2015]. Objective responses were observed in all tumor types and the majority are durable; this combination has been well tolerated with rates of irAEs that are similar to pembrolizumab monotherapy and low rates of treatment discontinuation due to irAEs [Gangadhar, T. C., et al 2017] [Hamid, O., et al 2017].

6. Study Population

Male/female participants with metastatic NSCLC, who express high levels of PD-L1 (TPS $\geq 50\%$), have received no systemic anti-cancer therapy for their metastatic NSCLC, and are at least 18 years of age will be enrolled in this trial.

Prospective approval of protocol deviations to recruitment and enrollment criteria, also known as protocol waivers or exemptions, is not permitted.

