
● Use the following scale of criteria as guidance (not all criteria must be present to be indicative of a study treatment relationship).
● Yes, there is a reasonable possibility study treatment relationship: There is evidence of exposure to the study treatment. The temporal sequence of the AE onset relative to the administration of the study treatment is reasonable. The AE is more likely explained by the study treatment than by another cause.● No, there is not a reasonable possibility of study treatment relationship: Participant did not receive the study treatment OR temporal sequence of the AE onset relative to administration of the study treatment is not reasonable OR the AE is more likely explained by another cause than the study treatment. (Also entered for a participant with overdose without an associated AE.)● For each AE/SAE, the investigator must document in the medical notes that he/she has reviewed the AE/SAE and has provided an assessment of causality.● There may be situations in which an SAE has occurred and the investigator has minimal information to include in the initial report to MSD. However, it is very important that the investigator always make an assessment of causality for every event before the initial transmission of the SAE data to MSD.● The investigator may change his/her opinion of causality in light of follow-up information and send an SAE follow-up report with the updated causality assessment.● The causality assessment is one of the criteria used when determining regulatory reporting requirements● For studies in which multiple agents are administered as part of a combination regimen, the investigator may attribute each adverse event causality to the combination regimen or to a single agent of the combination. In general, causality attribution should be assigned to the combination regimen (i.e., to all agents in the regimen). However, causality attribution may be assigned to a single agent if in the investigator's opinion, there is sufficient data to support full attribution of the adverse event to the single agent.
Follow-up of AE and SAE

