Continuous measures such as changes from baseline in laboratory, vital signs, and ECG parameters that are not pre-specified as Tier 1 endpoints will be considered Tier 3 safety parameters. Summary statistics for baseline, on-treatment, and change from baseline values will be provided by treatment group in table format.

[figure not shown]

[figure not shown]
Table 5 Analysis Strategy for Safety Parameters

[figure not shown]
| Safety Tier | Safety Endpoint                                                                        | p-Value | 95% CI for Treatment Comparison | Descriptive Statistics |
|-------------|----------------------------------------------------------------------------------------|---------|---------------------------------|------------------------|
| Tier 2      | Any AE                                                                                 |         | X                               | X                      |
|             | Any Grade 3 to 5 AE                                                                    |         | X                               | X                      |
|             | Any serious AE                                                                         |         | X                               | X                      |
|             | Any drug-related AE                                                                    |         | X                               | X                      |
|             | Any serious and drug-related AE                                                        |         | X                               | X                      |
|             | Any Grade 3 to 5 and drug-related AE                                                   |         | X                               | X                      |
|             | Dose modification due to AE                                                            |         | X                               | X                      |
|             | Discontinuation due to AE                                                              |         | X                               | X                      |
|             | Death                                                                                  |         | X                               | X                      |

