### 3.12 EXTENT OF EXPOSURE

Extent of exposure for a participant is defined as number of cycles in which the participant receives the study medication. Summary statistics will be provided on extent of exposure for the APaT population.

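### Should the plan say which of the two study drugs is counted for AE-related discontinuation and for extent of exposure?

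*Protocol*

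**What the plan says.** Protocol Section 4 lists as a secondary safety endpoint "Number of participants experiencing AEs and number of participants discontinuing study drug due to AEs". The analysis sections carry this forward without naming a drug:

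- Protocol 10.6.2 (Amendment 05) states that "dose interruption due to an AE and discontinuation due to an AE, will be summarized by counts and percentages by treatment group". Table 13 is descriptive only.
- sSAP 3.6.3, Table 5, has a Tier 2 row labelled "Discontinuation due to AE", marked under the column "95% CI for Treatment Comparison", with the Miettinen and Nurminen method for the interval.
- sSAP 3.12 reads "Extent of exposure for a participant is defined as number of cycles in which the participant receives the study medication". Protocol 10.12 uses the same wording.

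Elsewhere the two drugs are sometimes told apart. The PT/INR note in the Schedule of Activities (Protocol 2.1) asks for monitoring "weekly for first 4 weeks after initiation of therapy and upon DC of epacadostat/placebo". Appendix 4, on causality, says that "causality attribution may be assigned to a single agent".

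**The concern.** A participant could stop the capsule or tablet for an AE and stay on the infusion. That person is a discontinuation if a stop of any drug counts, and is not one if only pembrolizumab, or only stopping both drugs, counts. The row describes a listed secondary endpoint and carries a between-arm interval in the sSAP. An unwritten rule could in principle be picked after unblinding.

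Exposure raises a related question. Under Protocol 9.9.2 a cycle is the 21-day pembrolizumab interval, so a cycle can count in full however many days the oral drug was taken. The dose rationale in Protocol 5.5.2 relies on "inhibition of IDO1 achieved throughout the dosing period". After a negative ORR result, a reader will want to know whether epacadostat was taken well enough to test that idea, and a cycle count alone cannot answer.

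**Working it through.** The plan states no figure for these rows, so there is none to reproduce. The check sets the texts side by side and then sizes the ambiguity.

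**1. Is a counting rule written anywhere visible?** Protocol Section 7 defines study treatment to include every product given, placebo among them, but sets no any-drug or all-drugs rule. Protocol 8.1 treats discontinuation of study treatment as a single event, with unacceptable adverse experiences among the reasons. The Schedule of Activities sends anyone who discontinues study treatment straight to the end-of-treatment and safety follow-up visits. These passages lean towards the regimen as a whole. They are Amendment 05 text, written when only pembrolizumab remained, so they do not settle the earlier period.

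**2. Could the rule have stood in text that is no longer shown?** Yes. The sSAP was revised to match Amendment 04. Amendment 05 then removed the epacadostat dose-modification text from 7.2.1 and deleted 7.6.2 and 9.1.9.1.2, the natural places for a rule on stopping the oral drug. The visible sSAP numbering also runs from 3.6.3 to 3.6.5.

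**3. How far can the reading move the row?** Inputs: 74 per arm (Protocol 10.1, sSAP 3.1), taking the treated population as equal to the planned arm size, and an unstratified Miettinen-Nurminen 95% CI (sSAP 3.6.3). All event counts are assumed.

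One participant: 1/74 = 1.35 points.

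With 7 pembrolizumab stops per arm (7/74 = 9.5%), adding oral-only stops gives:

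| Oral-only stops, epacadostat / placebo | Any-drug counts | Difference (95% CI), points |
|---|---|---|
| 0 / 0 | 7 vs 7 | 0.0 (-10.2 to 10.2) |
| 5 / 0 | 12 vs 7 | 6.8 (-4.3 to 18.1) |
| 8 / 0 | 15 vs 7 | 10.8 (-0.7 to 22.7) |
| 9 / 0 | 16 vs 7 | 12.2 (0.5 to 24.2) |
| 9 / 1 | 16 vs 8 | 10.8 (-1.2 to 23.0) |
| 9 / 2 | 16 vs 9 | 9.5 (-2.8 to 21.8) |

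With no oral-only stops on placebo, the smallest number on epacadostat that takes the lower limit above zero is 8 for 4 pembrolizumab stops per arm, 9 for 7, 10 for 11 and 11 for 15.

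**4. Does crossing zero change a conclusion?** No. sSAP 3.6.3 presents these unadjusted intervals as a descriptive aid and says that they are not a formal significance assessment. It expects no Tier 1 safety events. Protocol Table 13 has no interval at all.

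**5. Is oral intake otherwise invisible?** From the end of enrolment (05-SEP-2018) to the data cutoff (10-JAN-2019) is 127 days, and 127/21 = 6.05. A participant first dosed on that last day and treated without a break would have 7 administrations (days 0 to 126), whatever the oral intake. The cycle count is coarse for a daily drug. But Protocol 10.11 and sSAP 3.11 collect drug accountability data and commit to reporting any departure from the directed administration, so missed oral doses have their own output.

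**The case for a change.** The best case for a change is that the terms really are undefined, and that usage points both ways. In the safety-population text (Protocol 10.5.2, sSAP 3.5.2), receiving incorrect study medication can in practice concern only the oral drug, because both arms get pembrolizumab. In the exposure text, the cycle is tied to pembrolizumab. Amendment 05 does not remove the ambiguity for the past: summaries remain by treatment group and pool the two-drug period with later pembrolizumab alone. The exposure point would stand even if the deleted rules had required both drugs to stop together. And extra rows would be cheap.

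Most of this stands as description. The visible wording names no drug, the exposure unit is coarse, and per-drug rows would be informative. What does not stand is the step to a defect in the plan. The case for a large effect assumes that oral-only stops fall almost entirely in one arm of a blinded, placebo-controlled comparison. The Schedule of Activities note is weak evidence of separate tracking, since a stop of epacadostat or placebo also occurs when both drugs stop. That the reading might be chosen after unblinding is possible, but nothing in the documents shows it; the case report form and table specifications are not part of them.

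**Conclusion.** The concern does not call for a change. The plan leaves a counting definition unwritten in descriptive summaries, and analysts fill such a gap routinely in table specifications, with the rule given in a footnote. Under the assumed counts above, the choice of reading shifts the between-arm difference by 1.35 points for each net reclassified participant. With 7 pembrolizumab stops per arm, the interval excludes zero only in the extreme split of nine or more oral-only stops against none, or a similar imbalance, and the sSAP attaches no inference to that. The primary ORR result and its error rate do not depend on the reading. New discontinuations after Amendment 05 are unambiguous, because only pembrolizumab is given.

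For exposure, cycles together with a compliance report are a fair trade-off. Days on the oral drug would add information without correcting a wrong result.

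This rests on the visible text, on 74 treated per arm, and on the compliance reporting being carried out as stated. The deleted Amendment 04 text may already have fixed the discontinuation rule; that cannot be confirmed from these documents.
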